#### 9. ANALYSIS POPULATIONS

The following analysis populations are planned for the studies:

- **Full Analysis Set (FAS)** will include all enrolled subjects who receive at least one dose of study medication and have at least one post efficacy assessment.
- **Safety Analysis Set (SAS)** will include all subjects who received at least one dose of study drug and had at least one post dose safety assessment.

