Dispense/Review/ Collect Patient Diary			X		X	X		X		X	X		X		X	
Study Drug Accountability		f (ICE	'11.1		X	X		X		X	X		X		X	

a. A copy of the informed consent form (ICF) will be given to the patient for review.

b. Signing of the ICF will occur during screening phase (Visit 1 or Visit 2) prior to conducting any study assessments.

c. Assessments to be done for early termination for any reason. Other assessments/procedures to be done at PI discretion, if necessary.

d. Assessments do not need to be performed if prior assessments were within one month of this early termination visit.

MediciNova Inc.

Final Protocol MN-001-IPF-201

Amendment 2 December 21, 2015

- e. Dispense Open-label study medications after all procedures and assessments have been completed. f. Lab retest assessments to be done for subjects with clinically significant abnormal lab findings. g. 12-lead ECG to be done at Hour 1.5 (\pm 30 minutes) post dose h. The 6 minute walk test should be performed twice during these visits.

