7.3.1. Individual Stopping Criteria

Subjects who experience an adverse event of Grade 2 nausea and/or diarrhea for greater than 3 consecutive days, or Grade 3 nausea and/or vomiting for greater than 1 day thought to be related to study drug will be discontinued from the study. Additionally, subjects who experience an adverse event of Grade 3 abdominal pain lasting for greater than 1 day thought to be related to study drug will be discontinued from the study.

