8.8.1.1. Screening Phase (Up to 3 months prior to Day 1)

Visit 1 (Day -90 to Day -8)

At any point during this time, subject may be approached for participation in the study. An informed consent form (ICF) will be given to the subject and the subject will be instructed to read the ICF and ask the study staff any questions they may have. The subject can either sign the ICF then or defer signing until they return for Study Visit 2.

Visit 2 (Day- 7 ± 5 days)

During the Screening Phase, once the informed consent form is signed, the following assessments will be performed/collected):

- Inclusion/Exclusion criteria review
- Medical history
- Physical examination
- Height/body weight
- Vital signs including supine blood pressure, respiratory rate, heart rate, and temperature
- 12 lead Electrocardiogram (ECG)
- Fasting safety labs chemistry (including CPK, liver enzymes, lipid panel) hematology, and urinalysis labs

- Serum β-hCG (pre-menopausal females)
- Blood Sample for biomarker
- Prior/concomitant medication review
- Pulmonary function test
- 6 minute-walk test (6MWT)*
- Dyspnea score (MMRC: Modified Medical Research Council Dyspnea Score)
- ATAQ-IPF (A Tool to Assess Quality of Life in IPF)

The results of pulmonary function test, 6MWT, MMRC and ATAQ-IPF at this visit are considered "Baseline" values.

* Two tests should be performed for 6MWT

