8.8.1.4 Follow-up / Laboratory Re-test Visits/ Early termination visit

Follow up clinic visit: Month 13 (\pm 5 days)

- Physical examination
- Body weight
- Vital signs including supine blood pressure, respiratory rate, heart rate, and temperature
- Adverse event review
- Concomitant medication review

Laboratory Re-test visit

Subjects who have clinically significant abnormal lab finding will return for a laboratory re-test visit and will have the following assessments performed:

- Fasting chemistry, hematology, or urinalysis lab, as indicated
- Adverse event review
- Concomitant medication review

Early Termination visit

Subjects who discontinued study medication will undergo the following assessments:

- Physical examination
- Body weight
- Vital signs including supine blood pressure, respiratory rate, heart rate, and temperature
- Adverse event review
- Concomitant medication review
- Patient diary review and collect
- Study drug accountability
- Study drug return
- 12-lead ECG**
- Fasting safety labs chemistry (including CPK, liver enzymes, lipid panel) hematology, and urinalysis labs**
- Urine β-hCG (pre-menopausal females)**
- Blood Sample for biomarker**
- Pulmonary function test**
- 6MWT**7
- Dyspnea score (MMRC)**
- ATAQ-IPF**
 - ** Assessment need not be performed if prior assessment occurred within 1 month of Early Termination Visit.

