13.1. Data Analysis

13.1.1. Analysis Populations

Full Analysis Set (FAS) will include all enrolled subjects who receive at least one dose of study medication, and have at least one post efficacy assessment.

Safety Analysis Set will include all subjects who received at least one dose of study drug and had at least one post dose safety assessment.

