### 9.1. Use of analysis populations in different analyses

Safety analyses will be conducted on the Safety Analysis Set, and subjects will be analyzed based on the treatment they received. Efficacy analysis will be conducted on the Full Analysis Set, and subjects will be analyzed based on the treatment to which they were randomized.

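### The Full Analysis Set can drop dosed subjects who leave before Month 1, and with them early worsening-IPF events

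*SAP*

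**What the plan says.** SAP 9 limits the FAS to enrolled subjects who take at least one dose and "have at least one post efficacy assessment". Protocol 13.1.1 carries the same condition ("and have at least one post efficacy assessment"). Neither document says which measure qualifies, or whether a worsening event counts.

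SAP 9.1 applies the set to every efficacy endpoint: "Efficacy analysis will be conducted on the Full Analysis Set, and subjects will be analyzed based on the treatment to which they were randomized". SAP 13.3 repeats this for the secondary endpoints, which include frequency of and time to first worsening IPF. Worsening covers acute exacerbation, respiratory hospital admission, IPF death and transplant (Protocol 8.8.2.11). Subjects free of worsening are censored at their last visit.

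In Protocol Table 1 and 8.8.1.2, the Week 1 call has no efficacy measure, Month 1 has MMRC only, and FVC, 6MWT and ATAQ-IPF are first repeated at Month 3. Their baseline values come from Visit 2, Day -7 ± 5 days (Protocol 8.8.1.1).

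For early termination, footnote d of Table 1 states: "Assessments do not need to be performed if prior assessments were within one month of this early termination visit". Protocol 8.8.1.4 repeats the waiver ("Assessment need not be performed if prior assessment occurred within 1 month of Early Termination Visit") for all four efficacy measures. Neither text requires the earlier assessment to be post-dose.

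**The concern.** Whether a subject enters the FAS depends on something that happens after randomisation, namely whether the subject stays long enough, or is tested on leaving. That can be related to treatment. Under Protocol 7.3.1, subjects with specified gastrointestinal events "thought to be related to study drug will be discontinued from the study", and such events can occur in the first weeks.

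For FVC the loss would hardly matter, since these subjects have no follow-up value. Worsening IPF is different. Its status is known from event reporting, so a subject with an early exacerbation, admission or death has valid outcome data whether or not an MMRC was recorded. The clause can discard that outcome for a reason unrelated to the endpoint. No planned analysis puts it back: the sensitivity analyses in SAP 13.2 and 13.4 use narrower subsets and do not cover the worsening endpoints.

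**Working it through.** **Arm sizes.** The target of about 15 has no power calculation behind it, so there is no figure to reproduce. At 2:1, 15 × 2/3 = 10 on MN-001 and 15 × 1/3 = 5 on placebo. One subject lost is 1/10 = 10% or 1/5 = 20% of an arm.

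**How long baseline values can satisfy the waiver.** Visit 2 falls between Day -12 and Day -2. The last day covered is the Visit 2 day plus one month.

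| Length of month | Visit 2 on Day -12 | Visit 2 on Day -2 |
|---|---|---|
| 28 days | Day 16 | Day 26 |
| 30 days | Day 18 | Day 28 |
| 31 days | Day 19 | Day 29 |

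If the calendar has no Day 0, each limit moves one day later. What counts is the date of the early-termination visit, not the date of the last dose.

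**First scheduled post-dose efficacy value.** This is the Month 1 MMRC, at 30 ± 5 days, so Day 25 to Day 35. A subject whose early-termination visit falls inside the waiver window can therefore leave with no post-dose efficacy value. A subject who dies before Month 1 has no early-termination visit and nothing scheduled before it.

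**FVC.** The ANCOVA at Months 3 and 6 needs a post-baseline FVC, so these subjects do not contribute to it under either definition. In the mixed model they would add only a baseline value. A subject with a Month 1 MMRC and no later FVC is already in the FAS in that position.

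**Worsening IPF, event-free early stopper.** Suppose the subject is censored by about Day 28 and nobody has had an event before then. The subject is in no log-rank risk set, so the test and the Kaplan-Meier curve are the same with or without that subject. Only the proportion moves: for example, 2/10 = 20.0% becomes 2/9 = 22.2%. Lost follow-up is at most about 4 weeks out of 10 × 26 = 260 subject-weeks in the MN-001 arm, or 1.5%.

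**Worsening IPF, early event.** An invented example, for illustration only: MN-001 events on Days 15, 18 and 110, one placebo event on Day 120, and everyone else followed to Day 182.
- All dosed subjects: 3/10 against 1/5. Expected MN-001 events = 10/15 + 9/14 + 8/13 + 7/12 = 2.51, so observed minus expected = 3 - 2.51 = +0.49.
- The two early events excluded: 1/8 against 1/5. Expected = 8/13 + 7/12 = 1.20, so observed minus expected = 1 - 1.20 = -0.20.

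The sign changes. It takes two such events in one arm to produce this.

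**How often an exclusion might arise.** The documents give no early-stop rate, so the rates below are assumptions. They also assume that every early stopper is excluded, which makes the results upper limits. P(at least one of 15) = 1 - (1 - q)^15.

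| Assumed rate q | P(at least one) | Expected number (15q) |
|---|---|---|
| 3% | 0.37 | 0.45 |
| 5% | 0.54 | 0.75 |
| 10% | 0.79 | 1.5 |
| 20% | 0.96 | 3.0 |

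**The case against.** The best counter-argument is that the clause may exclude nobody. Protocol 10 lists worsening IPF among the efficacy assessments, and SAP 13.3 identifies it through adverse events. Adverse events are reviewed at the Week 1 call and again at early termination, where that review is not waivable. On this reading an early stopper does have a post-dose efficacy assessment. The reading is possible, but the SAP does not adopt it, and a programmer could equally require an MMRC or FVC record.

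A reader might also infer more than the documents support:
- *That early stoppers will have no assessment.* The waiver only permits skipping, and Protocol 7.3 asks sites to try to complete the early-termination procedures.
- *That deaths leave through the waiver.* They do not. They would be lost because nothing is scheduled before Month 1, and only if an IPF death is not itself counted as an assessment.
- *That losses fall mainly on MN-001.* Protocol 4.2.1 does report more gastrointestinal events on drug (19% against 5% in the Phase 3 asthma study; 18.2% against 10.8% in the four-week asthma study). In the four-week study, however, none was severe and none led to discontinuation. There are no stopping data for this population.

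Worsening is not a listed reason for mandatory withdrawal, so a subject admitted early may still reach the Month 1 MMRC. Nor is anything hidden: SAP 11.1 gives analysis-set counts by arm and lists subjects in the Safety set but not the FAS, and deaths and serious events are listed. The endpoints are secondary, and SAP 10.6 treats p-values descriptively. These points limit the size of the problem. They do not justify keeping the clause.

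**Conclusion.** The point stands in a limited form. The clause can remove dosed subjects who leave before the Month 1 MMRC, through an early-termination visit up to about Day 18 to Day 28 or through early death. FVC results barely change. The exposure is in frequency of and time to first worsening IPF, where an early event could be dropped and denominators of about 10 and 5 reduced by 10% or 20% per subject. Event-free early stoppers mainly affect the denominators.

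This rests on two assumptions: that a worsening event is not treated as an efficacy assessment, and that sites use the waiver. The expected number of exclusions cannot be derived from the documents. The change is still worth making, because SAP 8 says the results will inform the design of later studies and the remedy is one clause.

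**What to change.** In SAP 9, define the FAS as all randomised subjects who took at least one dose, analysed as randomised. At minimum, use that set for frequency of and time to first worsening IPF. Time should run from Day 1, with event-free subjects censored at their last visit as SAP 13.3 already provides. If the clause is kept for other endpoints, state which assessments satisfy it. Record the change in SAP 15 before the treatment codes are opened, the point by which SAP 3 requires final approval.

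The cost is small. The ANCOVA is unchanged, and the mixed model gains a few baseline-only subjects. Crude worsening proportions will count briefly observed subjects as event-free, so they should be read beside the Kaplan-Meier estimates. The SAP will depart from Protocol 13.1.1 unless the protocol is amended, which needs written sponsor and IRB approval (Protocol 17.1). A documented departure in SAP 15 is the lighter route.

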### 9.1. Use of analysis populations in different analyses

Safety analyses will be conducted on the Safety Analysis Set, and subjects will be analyzed based on the treatment they received. Efficacy analysis will be conducted on the Full Analysis Set, and subjects will be analyzed based on the treatment to which they were randomized.

#### 10. GENERAL ISSUES FOR STATISTICAL ANALYSIS

Data from all clinical assessments will be listed and, where appropriate, summarized by treatment arms using descriptive statistics. Summary (descriptive) statistics of continuous variables include n, mean, standard deviation (SD), median, first quartile (Q1), third quartile (Q3), minimum and maximum values at each time-point. For categorical variables, the number and percent of counts will be presented.

#### 10.1. Definition of Treatment Arms

Treatment arms will be denoted as follows in the TLFs:

- "MN-001" 750 mg of MN-001 administered orally twice daily
- "Placebo" Matching Placebo administered orally twice daily
- "Former Placebo" Matching Placebo administered orally twice daily during the Double-Blind Treatment Phase and 750 mg of MN-001 administered orally twice daily during the OLE Phase

### **10.2.** Definition of Study Phases

Double Blind Treatment Phase (DBT Phase)

The DBT Phase starts with Visit 3 which is the Day 1 of the DBT phase.

The DBT Phase ends with end of the day of Visit 8 (Month 6) and assessments taken on this visit will be considered as belonging to the DBT phase.

Open Label Extension Phase (OLE Phase)

The OLE Phase starts on the following day of Visit 8 and ends with Visit 14(Month 13).

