8.8.1.2. Double-Blind Treatment Phase (26 weeks)

Subjects will enter the clinic in the morning prior to breakfast. Once the pre-dose fasting labs have been completed, subjects will be given breakfast except on Baseline Day 1.

Baseline Clinic Visit: Day 1

The following assessment will be done:

- Inclusion/Exclusion criteria review
- Vital signs including supine blood pressure, respiratory rate, heart rate, and temperature
- Urine β-hCG (in pre-menopausal females)
- Concomitant medication review
- Adverse event review
- Dispense study drug
- Dispense patient diary
- 12-lead ECG at Hour 1.5 (\pm 30 minutes) post dose

Once the pre-dose assessments have been completed, the subject will be administered the first dose of MN-001 (2 or 3 tablets of MN-001 250 mg) or matching placebo with water.

Clinic Visits: Months 1, 3 and 6* (± 5 days)

The following assessments will be done:

- Physical examination
- Body weight
- Vital signs including supine blood pressure, respiratory rate, heart rate, and temperature
- 12-lead ECG at Hour 1.5 (± 30 min) post dose

- Fasting safety labs chemistry (including CPK, liver enzymes, lipid panel) hematology, and urinalysis labs
- Urine β-hCG (pre-menopausal females)
- Blood Sample for biomarker (Month 6 only)
- Pulmonary function test (Months 3 and 6 only)
- 6MWT (Months 3 and 6 only)**
- Dyspnea score (MMRC)
- ATAQ-IPF (Months 3 and 6 only)
- Adverse event review
- Concomitant medication review
- Patient diary review
- Dispense study drug (Months 3 and 6 only)
- Study drug accountability
 - * Month 6 Clinic Visit is the start day (Day 1) of the Open-Label Extension (OLE) phase. All subjects will take MN-001 750 mg bid or 500 mg tid.
 - ** Two tests should be performed for 6MWT

Telephone Visits Week 1 (\pm 3 days) and Month 4 (\pm 5 days)

Between clinic visits, subjects will be called by a study team member (e.g., study coordinator or nurse) to collect information regarding their health status. The MMRC will be administered (only Month 4) and adverse events and concomitant medications will be documented.

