9.4. Study Drug Administration

The study drug will be dispensed by appropriately qualified site study staff as indicated on the delegation of authority log. Subjects will self-administer the study drug at home except on clinic visit days (Day1, Months 1, 3, 6, 7, 9 and 12). On those days, subjects will be instructed to wait until they come to the clinic to take their study medication. The subject will be instructed to return all unused study drug to the clinical trial site at each visit.

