### 10.3. Definition of Baseline

Unless otherwise specified, baseline is defined as the measurement closest to the date of the first administration of Investigational Medicinal Product (IMP), and preceding the first dose of IMP (MN-001 or Placebo).

For the DBT Phase, baseline values will be assessed pre-dose at Visit 3 (Day 1) in this study. For pulmonary function test, 6MWT, MMRC, ATAQ-IPF and 12-Lead ECG, the baseline values will be assessed at Visit 2 (Day -7).

For the OLE Phase, unless otherwise specified, baseline values for those subjects who were taking Placebo in the DBT Phase will be defined as measurements closest to the first administration of MN-001 and preceding the first dose of MN-001. Therefore, these baseline values will be the ones assessed pre-dose on Visit 8 (Month 6) of the DBT phase.

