#### 14.1. Adverse Events

Adverse events (AEs) will be coded using the Medical Dictionary for Regulatory Activities (MedDRA) central coding dictionary, version 21.0.

Summary tables for AEs will include treatment-emergent adverse events (TEAEs, defined as AEs occurred during or after the first administration of a study drug). AEs occurred before the first administration of a study drug will be listed separately. Aes occurring 7 days after the last dose of study medication will be listed separately.

Unless otherwise stated, AE analyses will be subject-based, each subject will be counted once in frequency tables at the subject, SOC and preferred term levels, and the denominator for percentages will be the number of subjects in the SAS, in the respective treatment arm (i.e. "as treated" assignment of treatment arms).

AEs will be assigned to study phases (DBT or OLE) based on their start date.

If the start date of an AE is incomplete:

a/ If only day is missing, and if in the same month the treatment was started then the start date of AE will be imputed with the day of first treatment. If treatment started earlier and not in that month then the first day of the month will be used for imputation.

b/ If month and day are missing, and the treatment start date was in the same year then the start date of AE will be imputed with the month and day of the first treatment administration. If the treatment start date was in the previous year, then 01 JAN will be used for imputation.

c/ If the entire AE start date is missing then the date will not be imputed, but the AE will be considered treatment-emergent.

If the end date of an AE is missing, the AE will be considered as "ongoing".

If a subject xperiences a TEAE with a missing causality assessment, then relationship will be categorized as "Related". AEs with a missing causality assessment during the screening period relationship will be categorized as "Unrelated".

If a subject experiences a TEAE with a missing severity assessment, then severity for this TEAE will be categorized as "Severe".

In addition to keeping the 5-level categorization of causality of AEs, they will also be dichotomized into two categories: related/not related. "Related" category comprises events which were classified by the investigator as possibly, probably or related to treatment, whereas "Not Related" category comprises the other two levels of the investigator's assessment ("Unlikely to be related" and "Unrelated").

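### Adverse events that start on the Visit 8 date after a former-placebo subject's first MN-001 dose are tabulated as double-blind placebo events

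*SAP*

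**What the plan says.** SAP section 10.2 ends the double-blind phase at the close of the Visit 8 day, treats that visit's assessments as double-blind data, and then says "The OLE Phase starts on the following day of Visit 8". SAP section 14.1 gives the only rule for placing an AE: "AEs will be assigned to study phases (DBT or OLE) based on their start date". SAP section 14 reports safety separately for the two phases. In SAP section 10.1, the Former Placebo label attaches MN-001 exposure to the extension phase only.

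Protocol section 8.8.1.2 draws the boundary elsewhere. A footnote to the Month 1, 3 and 6 visit list says "Month 6 Clinic Visit is the start day (Day 1) of the Open-Label Extension (OLE) phase" and continues "All subjects will take MN-001 750 mg bid or 500 mg tid". SAP section 10.3 agrees with the protocol here. For former-placebo subjects the extension baseline is the last value before the first MN-001 dose, and "Therefore, these baseline values will be the ones assessed pre-dose on Visit 8 (Month 6) of the DBT phase".

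Two other protocol passages bear on dosing that day. Section 9.4 includes Month 6 among the clinic-dosing days: "On those days, subjects will be instructed to wait until they come to the clinic to take their study medication". A note to the schedule of events in the synopsis says "Dispense Open-label study medications after all procedures and assessments have been completed".

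**The concern.** The SAP is inconsistent within itself, and not only with the protocol. Section 10.3 implies that a former-placebo subject first takes MN-001 on the Visit 8 day. Section 10.2 gives that whole day to the phase in which the same subject is labelled Placebo. SAP section 15, which lists departures from the protocol, does not mention this one.

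The treatment of first-day events is therefore uneven. In the MN-001 arm, an AE that starts after the first dose on Day 1 counts as an MN-001 event, because the double-blind phase begins at Visit 3. In the placebo arm, an AE that starts on the day of the subject's first MN-001 dose counts as a placebo event. At stake are the placebo column of the double-blind safety tables and the Former Placebo column of the extension tables. In a trial this small, a single subject moves either column visibly.

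**Working it through.** The documents state no figure on this point, so there is nothing to reproduce. The check is a reading of the rules followed by simple arithmetic.

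**Step 1: follow one event through the rules.** Take a former-placebo subject who receives the first MN-001 dose on the Visit 8 date and has an AE that begins later that day.

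| Rule | Source | Result |
|---|---|---|
| Extension starts on the Month 6 visit day | Protocol 8.8.1.2 | Extension event |
| First MN-001 dose follows the pre-dose Visit 8 baseline | SAP 10.3 | Event occurs on MN-001 |
| Double-blind phase runs to the end of the Visit 8 day | SAP 10.2 | Double-blind event |
| Phase is set by AE start date | SAP 14.1 | Double-blind event |
| MN-001 exposure of Former Placebo is in the extension only | SAP 10.1 | Arm in the double-blind phase is Placebo |

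The event is tabulated as double-blind, Placebo. The as-treated wording in SAP section 14.1 does not change this, because it settles the arm and not the phase, and it makes no exception for a day on which treatment changes.

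**Step 2: size per affected subject.** Inputs: about 15 subjects and 2:1 allocation (SAP section 6.1).

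- Placebo subjects: 15 × 1/3 = 5. MN-001 subjects: 10.
- Maximum shift in a placebo incidence per affected subject: 1/5 = 20 percentage points.
- If the placebo group has 4 subjects: 1/4 = 25 points. If it has 6: 1/6 = 16.7 points.
- Minimum shift: 0. SAP section 14.1.1 counts a subject once per preferred term per phase, so a subject who already had that event in the double-blind phase adds nothing.

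**Step 3: chance that it happens at all.** The documents give no rate of AEs starting on the first day of MN-001, so the rate p is an assumption. Taking 5 subjects who cross over independently, the chance that at least one is affected is 1 − (1 − p)^5.

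| Assumed p | Calculation | Chance of at least one |
|---|---|---|
| 2% | 1 − 0.98^5 | 9.6% |
| 5% | 1 − 0.95^5 | 22.6% |
| 10% | 1 − 0.90^5 | 41.0% |
| 20% | 1 − 0.80^5 | 67.2% |

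These chances fall if fewer than 5 placebo subjects complete the double-blind phase and cross over.

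**Step 4: which data could separate the events.** Protocol section 12.3 records AE onset time when it is known. Protocol section 9.5 lists dosing start and stop dates for the case report form, and SAP section 12.4 lists the start date of the dosing period. Neither document shows that the clock time of the first open-label dose is recorded.

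**The case against.** The best defence is that the time of the first MN-001 dose on the Visit 8 day is not settled. Subjects hold their dose until they reach the clinic, the Month 6 ECG is taken 1.5 hours after a dose, and open-label drug is dispensed only when all procedures are finished. Read together, the in-clinic dose could be the last blinded one, with MN-001 starting later that day. Keeping Visit 8 assessments in the double-blind phase would then be sensible, and only the remaining hours would be exposed. This argument stands as far as it goes. It shortens the window but does not close it, because protocol section 8.8.1.2 and SAP section 10.3 still point to a first MN-001 dose on that date.

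The defence also rightly limits the size. The window is at most part of one day in a 26-week phase (26 × 7 = 182 days). P values are descriptive under SAP section 10.6, and SAP section 14 plans no safety test.

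A reader might infer that all first-dose reactions after crossover are booked to placebo. The rules do not do that: reactions that begin the next day or later fall in the extension. A reader might also infer that such events are hidden. They leave the extension table, but SAP sections 14.1.2 and 14.1.3 list serious AEs and those leading to withdrawal, and section 10 lists data from all clinical assessments.

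The SAP cites protocol Amendment 1, whereas the protocol supplied is Amendment 2. The conflict between SAP sections 10.2 and 10.3 does not depend on which amendment applies.

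**Conclusion.** The concern holds for a narrow set of events: AEs in former-placebo subjects that start on the Visit 8 date after the first MN-001 dose. They are counted as double-blind placebo events and are missing from the extension count. For subjects continuing MN-001, only the phase label changes.

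Each affected subject can move an incidence by up to 20 percentage points, assuming 5 placebo subjects (16.7 to 25 points for 6 down to 4). It would be tempting to read 20 points as the expected distortion. The documents do not support that, because the shift can be zero and no first-day rate is given. Nor can it be said outright that the safety contrast is narrowed. That follows only if MN-001 raises the rate of the event in question.

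The conclusion rests on the first MN-001 dose being taken on the Visit 8 date, which protocol section 8.8.1.2 states and SAP section 10.3 implies. The point is worth correcting because the rule as written can change a reported count and the remedy is small.

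**What to change.** Amend SAP sections 10.2 and 14.1 as follows.

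1. For AE assignment only, the extension begins at the first open-label MN-001 dose. Visit 8 assessments made before that dose stay in the double-blind phase.
2. For an AE starting on the Visit 8 date, use the onset time where it is known and its order relative to the first open-label dose can be established.
3. Otherwise assign a former-placebo subject's AE to the extension, unless the record shows onset before the dose, for example because it was found during pre-dose procedures.
4. Flag every AE that starts on the Visit 8 date in a listing, so that the effect of the default is visible.

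The sponsor should also reconcile protocol section 8.8.1.2, protocol section 9.4 and the schedule note on open-label dispensing. They need to say whether the in-clinic Month 6 dose, and the ECG 1.5 hours after it, relate to double-blind or open-label drug. If that ECG follows open-label drug, it too carries a double-blind label under SAP section 10.2.

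The cost is a few sentences and one listing flag. The downside is that some pre-dose AEs with no recorded time could be attributed to MN-001; the Month 6 visit includes two walk tests and blood sampling, so such events are possible. Moving the whole day to the extension would make that error larger. Dose times may not be on the case report form, so the rule must be workable from dates alone.
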